*** Radioisotopes or Radiation Machines ***

You have not selected the Radioisotopes option in the General Checklist. If you would like to add Radioisotopes information, please select the option to enable this section.

4. Radioisotopes or Radiation Machines

In this section, investigators must enter all radiation usage associated with the protocol.

Important: Protocols that involve non-standard of care radioactive materials (which includes the terms "radioisotopes", "radionuclides", "radiopharmaceuticals", and "nuclear medicine studies", e.g., "PET", "MUGA", "Zevalin", and/or specific radionuclides such as "F-18", "Tc-99m", "Th-201", "I-131", "Ra-223", "Y-90", etc.) will receive review by the Radiation Safety Officer (RSO) and/or Radiation Safety Committee (RSC). In these cases, submission to the RSO/RSC should occur after the IRB staff has drafted the informed consent radiation exposure risk statement, or verified the statement that was drafted by the research team (as noted below*). For more information on how to submit for radiation safety review, see RSC instructions or contact the Radiation Safety Officer at [name].

(1) It is the responsibility of the PI to assure the accuracy and completeness of the data submitted in this section, consistent with guidelines provided below. (2) For projects requiring radiation procedures, please refer to this guidance.

- a) If applicable, list and quantify the radiographic diagnostic and therapeutic procedures associated with this protocol by clicking "Add" and adding to Table 1 below. (Includes X-ray, fluoroscopy, CT, radioactive materials, nuclear medicine, PET-CT, radiation oncology, accelerator, Cyber Knife procedures, etc.)

- b) Total estimated research radiation dose * :

* Calculate from the table above by adding the Effective Dose Subtotals for all procedures.

Protocol Title: Natural Procreative Technology Evaluation and Surveillance of Treatment for Infertility and Miscarriage

*NOTE: Informed Consent Radiation Exposure Risk Statement- The appropriate Informed Consent Radiation Exposure Risk Statement template language must be inserted into the SLU IRB Informed Consent, inclusive of applying the total estimated research radiation dose specified in item b) from the table above, as instructed in the SLU IRB Informed Consent Template. Per IRB Guidelines, the language will either be drafted by the IRB staff or drafted by the research team and then verified by IRB staff prior to submission to the RSC for review. Contact the IRB Office at [name] or [contact] with any questions.

*** Devices ***

5. Devices

a) Please list in the space below all investigational devices to be used on subjects during this study.

b) Please list in the space below all FDA approved devices to be used on subjects during this study.

*** Drugs, Reagents, Chemicals, or Biologic Products ***

6. Drugs, Reagents, Chemicals, Biologic Products, or Dietary Supplements, Vitamins, and Other Food Agents

Pilot
Phase III

Phase I
Phase IV

Phase II
 Not Phased

List placebo if it is considered a drug (contains more than inactive ingredients). For example, normal saline is considered a drug that should be listed, whereas placebo tablets are usually inert ingredients that do not need to be listed.

- b) Please list in the space below all investigational drugs, reagents or chemicals to be administered to subjects during this study. Attach all applicable Investigator Brochures in section #16 (Attachments).
- c) Please list in the space below all FDA approved drugs, reagents, chemicals to be administered to subjects during this study. Attach all applicable package inserts in section #16 (Attachments).
- d) Please list in the space below all dietary supplements, vitamins, minerals, or foods to be administered to subjects during this study.

Protocol Title: Natural Procreative Technology Evaluation and Surveillance of Treatment for Infertility and Miscarriage

*** Other Levels Of Review ***

7. Other Levels Of Review

1. University Radiation Safety

Protocols that involve non-standard of care radioactive materials (which includes the terms "radioisotopes", "radionuclides", "radiopharmaceuticals", and "nuclear medicine studies", e.g., "PET", "MUGA", "Zevalin", and/or specific radionuclides such as "F-18", "Tc-99m", "Th-201", "I-131", "Ra-223", "Y-90", etc.) will receive review by the Radiation Safety Officer (RSO) and/or Radiation Safety Committee (RSC). For information on how to submit for radiation safety review, see RSC instructions or contact the Radiation Safety Officer at [name].

- Not Applicable
 Yes, study involves radioactive materials

2. Institutional Biosafety

Experiments involving the deliberate transfer of Recombinant or Synthetic Nucleic Acid Molecules (e.g., Gene Transfer), or DNA or RNA derived from Recombinant or Synthetic Nucleic Acid Molecules, or Microorganisms containing Recombinant or Synthetic Nucleic Acid Molecules and/or infectious agents (including select agents and toxins as defined by CDC and/or Animal and Plant Health Inspection Service (APHIS)) into one or more human research participants must be reviewed by the SLU Biological Safety Officer. Most of these protocols also require review and approval by the SLU Institutional Biosafety Committee (IBC). Please contact the SLU Biological Safety Officer at [name] for more information.

- Not Applicable
 Yes, study requires Institutional Biosafety review

3. Pharmacy, Therapeutics, Nutrition, and Transfusion (PTNT) Committee

Saint Louis University Hospital requires that all research involving the administration of medications within the hospital (including outpatient areas such as the Emergency Department, Outpatient Center, Saint Louis University Hospital-South Campus, etc.) be reviewed and approved by the Pharmacy, Therapeutics, Nutrition, and Transfusion (PTNT) Committee and that study drugs are received, stored, prepared, and dispensed by the Hospital's Department of Pharmacy Services. Please contact the Investigational Drug Services Clinical Pharmacist at [name] or [contact] for more information.

- Not Applicable
 Yes, study requires PTNT review

Protocol Title: Natural Procreative Technology Evaluation and Surveillance of Treatment for Infertility and Miscarriage

4. Saint Louis University Hospital

All research involving Saint Louis University Hospital, including the Emergency Department, inpatient or outpatient services (including outpatient surgery at SLUH South Campus and the infusion center at the DOB) and medical record access, requires Research Business Review (RBR) and approval prior to study initiation. This process is designed to facilitate compliance with state and federal regulations as they pertain to research in hospitals and clinical research billing. While researchers can begin to complete the SSM RBR form at any time, the form should not be submitted until the IRB and the Clinical Trials Office (CTO) have approved the study. Please contact the Research Compliance Office at [name] or [contact] or the CTO at [name] or [contact] for more information.

- Not Applicable
Yes, study requires Saint Louis University Hospital review

5. SSMSL

All research involving SSMSL locations (including Cardinal Glennon), including inpatient or outpatient services and medical record access, requires approval from the SSM STL or SSM Cardinal Glennon Research Business Review (RBR) prior to study initiation. This process is designed to facilitate compliance with state and federal regulations as they pertain to research in hospitals and clinical research billing. While researchers can begin to complete the SSM RBR form at any time, the form should not be submitted until the IRB and the CTO have approved the study. Please contact the SSMSL Office at [name] or [contact] for more information.

- Not Applicable
Yes, study requires RBR review

6. Does this project require registration on ClinicalTrials.gov, and/or is this project subject to the NIH GCP Training Requirement? (Select "Yes" if either apply) Y

Registration may be required if any of the following apply: 1) The project meets the FDAAA definition of an "Applicable Clinical Trial", which requires registration on ClinicalTrials.gov. 2) As of January 1, 2017, a new NIH policy mandated biomedical and behavioral "Clinical Trials" to be registered on ClinicalTrials.gov. In addition, NIH policies require personnel on NIH "Clinical Trials" to take GCP training every three years. 3) Registering may be required for Journal Publication (ICMJE). Please review relevant definitions here. Contact the CTO at [contact] with questions about registering on ClinicalTrials.gov and refer to the training page of the IRB website for information on NIH GCP Training requirements.

*** Subject Population ***

8. Subject Population - In the space below, please detail the participants that you are requesting to recruit

Protocol Title: Natural Procreative Technology Evaluation and Surveillance of Treatment for Infertility and Miscarriage

(include description of each group requested)

- a) **Expected age range of subjects. (For example ≥ 18 yrs to 90 yrs).**

18-55yrs of age

- b) **Number of evaluable subjects to be accrued at SLU or SLU site (this includes all sites under the direction of the SLU PI).**

600 participants (300 women and 300 partners)

Exceeding the number listed here is a protocol violation. Prior IRB approval is required if additional participants are to be accrued. If applicable, this number should be consistent with your power analysis described in 3d.

- c) **Number of evaluable subjects to be accrued study wide. *?HELP?***

600 participants (300 women and 300 partners)

- d) **If including vulnerable populations (minors, pregnant women and fetuses, neonates, non-English speaking, economically or educationally disadvantaged, prisoners, adults temporarily or permanently unable to consent for themselves): 1) provide the rationale for the importance of including this population in the research, and 2) specify the measures being taken to minimize risks to potentially vulnerable subjects. Click on hyperlinks to access SLU Guidelines containing additional considerations and strategies for mitigating risks.**

NA

- e) **If women, minorities, or minors are not included, a clear compelling rationale must be provided unless not applicable. Examples for not including minors: disease does not occur in children; drug or device would interfere with normal growth and development; etc. If federally funded reference appropriate section of the sponsors protocol/grant. *?HELP?***

Women and minorities are included. Usually minors are not seen for infertility

- f) **If any specifically targeted subjects are students, employees, or laboratory personnel, specify the measures being taken to minimize the risks and the chance of harm to these potentially vulnerable subjects. See SLU Guidelines for additional considerations and strategies for mitigating risks.**

- g) **Describe (labeled a-c): a) who you are recruiting for this study (e.g., your patients/students/colleagues, those in existing database or registry, the general public), and b) how you are recruiting (flyers, advertisements, direct call/mailing, membership networks, in-person recruitment in clinic, classroom, public locations, etc.). For secondary data analysis or specimen studies, state how you have access to materials. Importantly: do not contact participants prior to obtaining IRB approval for your study.**

c) **Also indicate whether or not you plan to obtain personal/private information or biospecimens for the purpose of screening, recruiting, or determining eligibility of prospective subjects prior to obtaining informed consent and how (obtained by communicating with prospective subjects or obtained by accessing records or stored biospecimens). Note: if you are accessing medical records other than those of your own patients or those in your immediate department, you will need to submit a HIPAA Preparatory to Research form and submit to the SLU Privacy Officer PRIOR to accessing records.**

Protocol Title: Natural Procreative Technology Evaluation and Surveillance of Treatment for Infertility and Miscarriage

Please refer to the SLU IRB Recruitment Guidelines when designing recruitment strategies and upload recruitment materials to the Attachments page for IRB review. You are expected to obtain permission for individuals/organizations that assist with recruitment, and whenever possible, those assisting should share your materials with potential participants on your behalf rather than providing you with private contact information.

Couples seeking NPT treatment or consultation to achieve pregnancy, to maintain pregnancy, or for fertility-related health issues will be recruited from our practice. Providers will present the study information to the patients at any visit. Women and their partner do not have to be consented at the same visit on the same date. No recruitment by phone or mail will be done.

*** Subject Population ***

8. Subject Population (continued)

Page numbers from a sponsor's protocol/grant may be referenced in 8h.

h) Inclusion and Exclusion Criteria.

Identify inclusion criteria.

1. Couple or women, seeking NPT treatment or consultation to achieve pregnancy, to maintain pregnancy, or for fertility-related health issues.
2. Couple or women who is seeking pregnancy WITHIN the coming year.

Identify exclusion criteria.

1. Couple or women is not a candidate for NPT for pregnancy (for example, couple or women is medically sterile or medically too high risk for pregnancy).
2. Couple or women is not able to provide informed consent (for example, language barriers).

i) Compensation. Explain the amount and schedule of compensation, if any, that will be paid for participation in the study. Include provisions for prorating payment.

No compensation will be paid

j) Describe who will cover study related costs. Explain any costs that will be charged to the subject.

Neither the subject or their insurance company will be billed for any study related procedures.

k) Estimate the probable duration of the entire study including data analysis and publication. This estimate should include the total time each subject is to be involved and the duration the data about the subject is to be collected. If the study is Investigator-initiated, a timeline for individual subject recruitment, follow-up, total time for subject accrual, and data analysis for the study is required.

Annual questionnaires will be sent out to consented participants yearly for 3 years
We anticipate keeping the study open for up to 10 years for enrollment.

Couple/Female involvement 3 years

Data collection per couple 3 years

Analysis and publication 3 years

Total duration of study 19 years

Protocol Title: Natural Procreative Technology Evaluation and Surveillance of Treatment for Infertility and Miscarriage

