This study involves research, and the purpose of this study is to evaluate live birth rates among couples who are treated by Natural procreative technology, (NPT) for infertility and miscarriage.

Comparisons will be made to those declining NPT treatment, waiting for NPT treatment, receiving other treatment, or stopping treatment. We seek to document specific pregnancy rates for different factors such as age and type of infertility diagnosis. We will also assess characteristics of environmental exposures that may be associated with infertility. Couples will be followed for up to three years, regardless of when they begin NPT treatment, or whether they continue treatment. We are seeking the broadest possible participation from couples who are considering NPT treatment. Data from all couples will be useful for this study, regardless of their individual circumstances or actual treatment.

Page numbers from a sponsor's protocol/grant may be referenced in 2b and 2c.

Protocol Title: Natural Procreative Technology Evaluation and Surveillance of Treatment for Infertility and Miscarriage

b) List your research objectives (specific aims & hypotheses of the study).

This is an exploratory study rather than a hypothesis testing study. This study aims to determine what the live birth rates are over time for patients who are treated with natural procreative technology (NPT) for infertility or history of spontaneous abortion, and how the live birth rate may vary by patient characteristics, especially the age of the woman, prior pregnancy, and underlying diagnoses. Secondary analyses will explore outcomes of conceptions (live birth versus other outcomes) and the association of environmental exposures with infertility. This is an observational study: there will be no intervention. Patients will receive whatever care they choose to receive. Couples receiving NPT treatment will be compared to those declining NPT treatment, waiting for NPT treatment, receiving other treatment, or stopping treatment. Interventions received, conceptions, and outcomes of conceptions will be followed for up to 3 years for each couple entering the study.

Please save frequently

c) Describe the study design (e.g., single/double blind, parallel, crossover, control, experimental, observational, etc.). If the study is investigator-initiated, a timeline for individual subject recruitment, follow-up, and analysis for the study is required. Also, indicate if the subjects will be randomized.

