- d) Describe how data analysis will be performed (statistical tests, methods of evaluating data) and indicate the smallest group/unit for which separate reporting will occur. For studies involving a questionnaire, if data and reliability information are available, please describe or provide references. For full board, unfunded studies describe sample size determination and power analysis. If none, please justify.

The database exists in Microsoft Access. Analyses will be done in Excel (for basis of descriptions), SAS and/or SPSS statistical computer programs. As stated above, data used in the analysis will be aggregate data, and will not contain any individual identifiers. Therefore, there will be no possibility of identifying individual respondents during the analysis or in the reporting of the final results.

Analysis of Main Outcome

The main outcome of this study is the proportion of subjects that had a live birth at various time points up to five years after beginning treatment with NPT, compared to couples who do not receive NPT treatment, or who cease to receive NPT treatment. This will be analyzed by standard lifetable techniques to deal with censored data (i.e., couples for whom pregnancy status cannot be ascertained beyond a certain time period). Cox proportional hazards regression will be used in an exploratory manner to investigate demographic and medical characteristics (particularly woman's age, prior pregnancy, and associated medical diagnoses) that may be associated with a greater likelihood of successful live birth. The same set of analyses will be repeated for the secondary outcome of conception (clinical pregnancy).

Analysis of Secondary Outcomes

Initially, all secondary outcomes will be analyzed as simple proportions, e.g., of couples who conceived, what proportion had a live birth, spontaneous abortion, or other pregnancy outcome.

Protocol Title: Natural Procreative Technology Evaluation and Surveillance of Treatment for Infertility and Miscarriage

conceived, what proportion had a live birth, spontaneous abortion, or other pregnancy outcome. Where indicated by the initial analysis, supplementary analyses using standard statistical techniques may be employed (e.g., a logistic regression with the outcome of live birth versus other pregnancy outcome).

Sample Size

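### The entry criteria require neither infertility nor prior miscarriage, and the main life table does not separate reasons for entry, so the headline live birth rate may not describe the population in the objective

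*Combined protocol and SAP*

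**What the plan says.** The objective in section 2b concerns "patients who are treated with natural procreative technology (NPT) for infertility or history of spontaneous abortion". The same sentence adds an interest in how the rate varies with the woman's age, prior pregnancy and underlying diagnoses. The lay summary in section 2a states an intention to give pregnancy rates by age and by type of infertility diagnosis.

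Section 8h has two inclusion criteria. The first is "Couple or women, seeking NPT treatment or consultation to achieve pregnancy, to maintain pregnancy, or for fertility-related health issues". The second is "Couple or women who is seeking pregnancy WITHIN the coming year". The first exclusion criterion reads "Couple or women is not a candidate for NPT for pregnancy", with sterility and excessive medical risk as its examples. The second concerns inability to consent. The breadth is intended: section 2a says "We are seeking the broadest possible participation from couples who are considering NPT treatment".

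Section 3d states: "The main outcome of this study is the proportion of subjects that had a live birth at various time points". It contrasts couples on NPT with couples who never receive it or who stop. The method is a life table, followed by an exploratory Cox regression on characteristics that include age, prior pregnancy and associated diagnoses. The same analyses are repeated for conception.

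**The concern.** A rate needs a denominator that matches the question. Section 2b names the denominator, but nothing in 8h or 3d enforces it. A couple who have just begun trying, have had no loss and want an NPT consultation satisfies both inclusion criteria and neither exclusion criterion. Their births would count in the headline proportion on the same footing as those of a couple with long-standing infertility.

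Two results are at stake. The first is the live birth proportion among NPT couples, which will be read as the result of treating infertility or prior miscarriage. The second is the comparison with couples not on NPT: if reasons for entry differ between the exposure groups, a difference can appear with no treatment effect. Even without couples outside the objective, the two named indications (difficulty conceiving, and difficulty carrying a pregnancy) are merged into one curve.

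**Working it through.** **Does any part of the plan tie the main result to the objective's population?**

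- Inclusion (8h): no duration of trying, infertility diagnosis or prior loss is required.
- Exclusion (8h): removes couples unsuited to NPT for pregnancy or unable to consent. It does not remove couples without infertility or loss.
- Definitions: the text defines neither infertility nor prior miscarriage, and it defines no analysis set.
- Main analysis (3d): split by NPT exposure only.
- Cox model (3d): exploratory. It gives hazard ratios, not a live birth proportion. Prior pregnancy and associated diagnoses do not by themselves identify who was infertile or had miscarried.
- Rates by diagnosis (2a): intended, but 3d contains no analysis that produces them.

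So no part does.

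**Size for a single rate.** The plan has no rate or power calculation to reproduce. Let f be the share of couples with neither indication, p_t the live birth proportion in the target population and p_o that in the others. Then

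pooled rate = (1 − f)·p_t + f·p_o, and overstatement = f·(p_o − p_t).

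The documents give none of these three values, so all are assumed. Overstatement in percentage points:

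| p_t | p_o | f = 10% | 20% | 30% | 40% |
|---|---|---|---|---|---|
| 30% | 60% | 3 | 6 | 9 | 12 |
| 30% | 70% | 4 | 8 | 12 | 16 |
| 30% | 80% | 5 | 10 | 15 | 20 |
| 40% | 60% | 2 | 4 | 6 | 8 |
| 40% | 70% | 3 | 6 | 9 | 12 |
| 40% | 80% | 4 | 8 | 12 | 16 |
| 50% | 60% | 1 | 2 | 3 | 4 |
| 50% | 70% | 2 | 4 | 6 | 8 |
| 50% | 80% | 3 | 6 | 9 | 12 |

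Example: 0.8 × 40% + 0.2 × 70% = 46%, which is 6 points above 40%. With f = 0 the shift is 0.

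**Against sampling error.** The 95% half-width is 1.96·√(p(1 − p)/n). At p = 40%:

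- n = 300 women (planned, section 8b): 1.96·√(0.24/300) = 5.5 points.
- n = 45 women (enrolled, continuing review form): 1.96·√(0.24/45) = 14.3 points.

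With rates of 40% and 70%, the shift passes 5.5 points once f exceeds 5.5/30 = 18%. With 45 women it stays inside 14.3 points over the whole assumed range of f. Only the most extreme cells of the table exceed the half-width at 45 women.

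**Size for the comparison.** Take rates of 40% and 70% and no treatment effect. With f = 10% in one exposure group and 30% in the other, the pooled proportions are 0.9 × 40% + 0.1 × 70% = 43% and 0.7 × 40% + 0.3 × 70% = 49%. The apparent hazard ratio is ln(1 − 0.43)/ln(1 − 0.49) = 0.83, or 1.20 with the groups reversed. For 10% against 40% (43% and 52%), it is 0.77.

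**The case against.** The strongest defence is that this is a deliberately broad, exploratory, observational cohort, and that sections 2a and 2b already show an interest in results by diagnosis. That stands as far as it goes: broad entry is a legitimate choice and the plan does not ignore diagnosis. But 2b still sets out to determine a rate in a named group, and 3d never produces it.

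Several stronger readings are tempting, and the documents do not support them.

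- A reader might infer that all couples go into a single undivided life table. Section 3d compares exposure groups. The pooling is across reasons for entry within each group.
- A reader might infer that the reported rate is bound to be wrong. NPT is described in section 1a as an approach to treating infertility, and every enrolled couple may have had one of the two indications. In that case the denominator matches the objective.
- A reader might measure the distortion against infertile couples alone. That is the wrong benchmark: fertile couples with a prior miscarriage belong to the objective's population.
- A reader might infer from the words on maintaining pregnancy that women already pregnant are admitted. The second inclusion criterion points the other way, section 8d (which asks about pregnant women) is answered as not applicable, and the phrase fits women with past losses who plan another pregnancy. Consent at any visit leaves some uncertainty but does not establish an error.

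A fair practical objection is precision. With 45 women, splitting by indication gives very wide intervals: a group of 15 at 40% has a half-width of 1.96·√(0.24/15) = 25 points. That argues for showing counts and intervals. It does not make the pooled figure an answer to 2b.

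**Conclusion.** The concern holds as a mismatch between objective, entry criteria and main analysis. Followed as written, 3d can report a rate for a different and mixed population, and nothing else in the plan corrects this. How far the rate departs from the target is unknown. It is 1 to 20 points too high under the assumed ranges (target 30–50%, others 60–80%, share 10–40%), and not off at all if every couple had a named indication. The upward direction rests on the assumption that couples with neither indication have the higher live birth rate. The effect on the NPT comparison further requires the mix to differ between exposure groups. At the planned size the shift can exceed sampling error; at the enrolled size it mostly would not, but it would still bias the estimate. The change should be made, and it remains possible because only data analysis is outstanding.

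**What to change.** In section 3d:

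1. Classify each couple at entry, from the entrance questionnaire and medical record, as infertility; prior spontaneous abortion without infertility; or neither. State one definition for each. The forms are attachments not reproduced in the text, so first confirm that they capture what is needed.
2. Make couples with either named indication the primary analysis set.
3. Show life tables by indication within NPT-exposure groups, with numbers at risk and confidence intervals.
4. Report couples with neither indication separately, and keep the all-couples curve as a secondary result.
5. As a check, see whether the records show any woman already pregnant when NPT began. If so, leave her out of the time-to-conception analysis.

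The cost is a revision of the analysis text and classification from data already collected. The downside is small groups and wide intervals with 45 women, so results by indication should be presented as descriptive.
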